BACKGROUND	Atrial fibrillation is the most frequent heart rhythm disorder. Its symptomatic forms, resistant to drug therapy, require invasive management (catheter ablation), which exposes to potentially serious complications including thromboembolic complications. Despite anticoagulant treatment, intra-atrial thrombus, which is a contraindication to catheter ablation, is detected in nearly 2 % of cases. Its diagnosis requires prior transoesophageal echocardiography, an unpleasant examination. The previous EXTRALUCID-d study showed that a zero ATE score, defined by no heart failure, no hypertension, no history of stroke, d-dimer < 270 ng/mL, has a negative predictive value of 100 % for the exclusion of intra-atrial thrombus.
PRIMARY OBJECTIVE	The objective of the study is to confirm the negative predictive value, sensitivity and specificity of the ATE score for the exclusion of intra-atrial thrombus.
SECONDARY OBJECTIVE(S)	
 • To determine the prevalence of atrial thrombi in the study population, • To determine the negative predictive value of the CHADS2VASC score of cardiac thrombus risk in the study population, • To determine the negative predictive value of the CHADS2 score of cardiac thrombus risk in the study population, • To collect a biobank of plasma samples to further confirm the study performances with other D-dimer assays.
OUTCOME(S)	The primary outcome is the number of patients with intra-atrial thrombus diagnosed by pre-procedural transoesophageal echocardiography.

STUDY TYPE	Prospective, multicentre diagnostic accuracy study in a standard of care setting.
MAIN INCLUSION CRITERIA	
 • Adult patients • Patients hospitalized for ablation of atrial fibrillation or symptomatic left atrial tachycardia • Affiliated person or beneficiary of a social security system • who have signed or orally given an informed consent
MAIN EXCLUSION CRITERIA	
 • Contraindication to transoesophageal echocardiography • Transoesophageal echocardiography made in another centre than the centre of ablation • Vulnerable persons • Refusal to participate in the study
INTERVENTION	
Patient management (preoperative assessment, intervention, surveillance, and follow-up) is carried out according to centre standard procedures.
 
An additional blood sample (7.2 ml) is collected for the d-dimer assay and the constitution of a biocollection.

TOTAL NUMBER OF SUBJECTS	3,000 patients
DURATION OF THE STUDY	
Duration of inclusion: 30 months
 
Duration by subject: at most 48 hours (from enrolment to transoesophageal echocardiography result)
 
Total expected duration of the study: 30 months

STATISTICAL ANALYSIS	
Sensitivity, specificity, positive predictive value, negative predictive value, and 95 % confidence intervals will be calculated.
 
The ATE score will be considered clinically relevant if a negative predictive value of 100 % is obtained for a zero score.

EXPECTED RESULTS	
This study is expected to confirm the negative predictive value of the ATE score.
 
This score could be proposed for the diagnosis of exclusion of intra-atrial thrombus in patients hospitalized for atrial fibrillation ablation or left atrial tachycardia. A zero score would avoid the systematic transoesophageal echocardiography.

CONTENT

Protocol revision history	2
1. Definitions and abbreviations	8
2. Contacts	9
3. Scientific justification and general description	10
3.1. Background	10
3.1.1. Pathology	10
3.1.2. Description of the ATE score to be validated	11
3.1.3. Description of the reference method	11
3.2. Study hypothesis and expected results	12
3.3. Overall risk/benefit assessment.....	12
3.4. Justification of low interventional level.....	12
4. Validation study objectives	13
4.1. Primary objective	13
4.2. Secondary objectives	13
5. Outcomes.....	14
5.1. Primary outcome	14
5.2. Secondary outcome.....	14
6. Study design	15
7. Study population	16
7.1. Inclusion / Exclusion criteria for intended population.....	16
7.2. Feasibility and recruitment modalities.....	16
8. Material and Methods.....	18
8.1. Transoesophageal echocardiography	18
8.2. D-dimer assay	18
8.2.1. Material	18
8.2.2. Method	18
8.2.3. D-dimer assay.....	18
8.3. ATE Score	19
8.4. CHADS ₂ and CHA ₂ DS ₂ VASC scores	19
9. Clinical data collection and procedure description.....	20
9.1. Study calendar	20
9.2. Data collection requirements	20
9.3. Screening	20
9.4. Enrolment	20
9.5. Visit 1.....	21
9.6. Patient exit.....	21
9.7. Constraints related to the research.....	21
9.8. Blood sample collection.....	21
10. Study follow-up.....	23
10.1. Protocol deviations	23
10.2. Adverse event reporting	23
10.2.1. Definition.....	23
10.2.2. Description of expected SAE	25
10.2.3. Event review and reporting	25
10.2.3.1. Event review	25
10.2.3.2. Reporting	25
10.2.4. Information for data collection.....	25

10.2.5. Quality control	25

3.1. Background

3.1.1. Pathology

Atrial fibrillation is the most common heart rhythm disorder, and is associated with increased mortality and morbidity, including through its thromboembolic complications. The invasive treatment of atrial fibrillation by catheter ablation is indicated in symptomatic and recurrent forms. Catheter ablation of atrial fibrillation is one of the most complex procedures in electrophysiology. Thromboembolic events are part of the complications and are responsible for cerebral (stroke or transient ischemic attack), coronary and peripheral arterial ischemia. Emboli may be due to thrombus or air, and their incidence varies between 0.28 and 2.8 % (1–5).

Cruoric embolisms are the most alarming on clinical level, and the most difficult to prevent. Several mechanisms are involved:

- Thrombus may result from blood coagulation cascades secondary to the introduction and handling of catheters (6). Ren *et al* reported an incidence of 10 % of left intra-auricular thrombus detected on transept sheaths or circular catheters (LASSO) introduced during ablation despite an effective anticoagulation (activated clotting time > 250 s). These thrombi have been detected with cardiac echocardiography (7). An important anticoagulation, activated clotting time > 300 s and infusion of the transseptal sheaths with a high flow rate (> 180 ml/h), significantly reduces the formation of thrombus and the occurrence of thromboembolic events (8).
- Endothelial lesions secondary to radiofrequency applications are also responsible for blood coagulation. The incidence of thromboembolic events is important when asymptomatic ischemic brain lesions are investigated by magnetic resonance imaging (MRI) after the ablation procedures. The type of energy used to create the ablation lesion affects this incidence. A study examined the effect of atrial fibrillation ablation technique on thromboembolic events. The number of recent asymptomatic ischemic lesions seen in MRI was greater in patients with atrial fibrillation ablation by non-irrigated multi-electrode radio-frequency compared to those who had cryotherapy ablation or conventional radiofrequency catheter ablation (9). These strokes were more often found in the vertebrobasilar territory, which is strongly suggestive of a cardioembolic origin.

- The thromboembolic mechanism may also correspond to the detachment of a pre-existing thrombus localized in the left atrium. The incidence of these thrombi is close to 2 % in the pre-procedural period, with values ranging from 1.2 % to 3.6 % (10–15).

The embolic risk is limited by performing imaging tests in order to eliminate the presence of a left atrial thrombus. The reference examination is the transoesophageal echocardiography which is an unpleasant examination.

3.1.2. Description of the ATE score to be validated

A preliminary study, EXTRALUCID-d (NCT02199080), included 2,494 patients hospitalized for an atrial fibrillation ablation. It studied a combined clinical-biological score, the Atrial Thrombus Exclusion (ATE), associating thromboembolic risk factors (hypertension, cardiac insufficiency, history of stroke) and d-dimer level for the prediction of intra-atrial thrombus.

The primary outcome was the number of intra-atrial thrombus diagnosed by transoesophageal echocardiography. A zero ATE score, defined by no cardiac insufficiency, no hypertension, no history of stroke, and D-dimer < 270 ng/mL, had a negative predictive value of 100% for the diagnosis of intra-atrial thrombus.

3.1.3. Description of the reference method

Transoesophageal echocardiography is performed routinely in more than 72 % of centres that perform atrial fibrillation ablation (16). It has a low morbidity. Most studies reporting transoesophageal echocardiography complications concerned examinations performed at cardiovascular operating room (17). Insertion and manipulation of the probe can damage the oropharynx, oesophagus or stomach. Two mechanisms of oesophageal lesions have been described, the first being a direct trauma occurring after insertion or manipulation of the endoscope. The second comes from the probe thermal energy. A multicentre study in cardiology described 10,419 transoesophageal echocardiographies where 88.7 % of patients were conscious and most of them did not receive sedation. In 1.9 % of cases, the probe could not be inserted because of a lack of patient cooperation (98.5 %) or due to anatomical reasons (1.5 %). In 0.88 % of the cases, when the endoscope was introduced, the examination had to be interrupted due to poor tolerance of the endoscope, pulmonary or cardiac complications or haemorrhage. Pre-transoesophageal echocardiography sedation complications have been described: hypoxia and transient hypotension (18). Transoesophageal echocardiography is recommended prior to any left atrium ablation in patients with persistent atrial fibrillation or with paroxysmal atrial fibrillation lasting longer than

48 hours when anticoagulation has not been satisfactory for more than three weeks. **The most recent recommendations on atrial fibrillation ablation (19) state that it was not possible to find a consensus on the indication of transoesophageal echocardiography in patients under well-conducted anticoagulant therapy.**

3.2. Study hypothesis and expected results

This study is lead in an independent population from the previous EXTRALUCID-d study in order to confirm the accuracy of the ATE score.

3.3. Overall risk/benefit assessment

We believe that the benefit / risk balance is very favourable, given that the risk of the study is negligible. The confirmation of an excellent negative predictive value of the ATE score would prevent one transoesophageal echocardiography out of three during the period of preoperative endocardial ablation of atrial fibrillation.

3.4. Justification of low interventional level

In addition to current practice, this study involves blood sampling. The collected volume complies with the conditions described by law for low interventional level (« Arrêté du 2 décembre 2016 fixant la liste des recherches mentionnées au 2^o de l'article L.1121-1 du code de la santé publique » for French law).

4. Validation study objectives

4.1. Primary objective

The objective is to confirm the negative predictive value, sensitivity and specificity of the ATE score for the exclusion of cardiac thrombus.

4.2. Secondary objectives

- To determine the prevalence of atrial thrombi in the study population,
- To determine the negative predictive value of the CHADS2VASC score of cardiac thrombus risk in the study population,
- To determine the negative predictive value of the CHADS2 score of cardiac thrombus risk in the study population,

To collect a biobank of plasma samples to further confirm the study performances with other D-dimer assays in the future.

5. Outcomes

5.1. Primary outcome

The primary outcome is the number of patients with atrial thrombus diagnosed by pre-procedural transoesophageal echocardiography.

Detection of spontaneous echocardiographic contrast will not be considered for the primary outcome. In case of cardiac thrombus, data will be recorded and transmitted to the sponsor after de-identification. The maximum time between transoesophageal echocardiography and ablation will be 48 hours. It may also be performed at the beginning of the procedure. The detection of a thrombus prohibits the realization of catheter ablation. In other words, if there is any doubt about the existence of a thrombus (equivocal image) the primary outcome is the contraindication to the intervention. If necessary, this definition may be reviewed according to the evolution of ultrasound images and the diagnosis (persistence of the initial image under increased anticoagulant treatment, decision of the medical team to practice intervention). This revision of the diagnosis will be decided by the medical team in charge of the patient.

5.2. Secondary outcome

- Number of atrial thrombi in the study population
- Number of patients with atrial thrombus among patients with a zero CHADS2VASC score (no congestive heart failure, hypertension, diabetes mellitus, vascular disease [previous myocardial infarction, peripheral arterial disease or aortic plaque], history of stroke or transient ischemic attack, age under 75, and male)
- Number of patients with atrial thrombus among patients with a zero CHADS2 score (no congestive heart failure, hypertension, diabetes mellitus, history of stroke or transient ischemic attack, and age under 75)

6. Study design

This is a European multicentre prospective diagnostic accuracy study.

[figure not shown]

Figure 1 : Study design. TEE: transoesophageal echocardiography

7. Study population

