8.4. CHADS₂ and CHA₂DS₂VASC scores

CHADS ₂ -> CHA ₂ DS ₂ VASC	
CHADS₂ Risk	Score
CHF	1
Hypertension	1
Age > 75	1
Diabetes	1
Stroke or TIA	2
From ESC AF Guidelines http://escardio.org/guidelines-surveys/esc-guidelines/GuidelinesDocuments/guidelines-afib-FT.pdf	
CHA2DS2-VASC Risk	Score
CHF or LVEF ≤ 40%	1
Hypertension	1
Age ≥ 75	2
Diabetes	1
Stroke/TIA/Thromboembolism	2
Vascular Disease	1
Age 65 - 74	1
Female	1

CHADS₂ and CHA₂DS₂VASC scores are stroke risk stratification schemes based on a risk factor approach (21–23).

9. Clinical data collection and procedure description

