9.4. Enrolment

During the inclusion visit, the investigator informs the participant and answers all questions about the objectives, nature of constraints, foreseeable risks and expected benefits of the

research. He also specifies the rights of the participant and verifies the eligibility criteria. Oral consent of the patient will be recorded in the medical file.

Medical history, clinical data and demographics are collected (hypertension, diabetes, congestive heart failure, age, history of stroke, peripheral arterial disease and diagnosis).

Peripheral blood sample is collected for d-dimer assay.

9.5. Visit 1

The transoesophageal echocardiography is performed no more than 48 hours before ablation or during the ablation procedure. The vacuity of the left atrial appendage or the presence of a thrombus is specified on the transoesophageal echocardiography report. A spontaneous contrast and emptying velocity may be mentioned but these data are optional. Pictures of the left atrial appendage are recorded on CD if a thrombus is diagnosed.

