11.1. Sample size rationale

Given the low rate of atrial thrombi (about 2 % of patients eligible to atrial fibrillation ablation), this study requires a high number of participants in order to allow reliable estimation of diagnostic performance.

To detect a 0.5 % deviation between two negative predictive values (binomial test), 2,000 patients are required for a power of 70 %; 2,400 patients for a power of 80 %; and 3,000 patients for a power of 90%.

Due to the high enrolment capacities of this multicentre study and its simplicity for the centres involved, it was chosen to focus on the power of the study and to retain a sample size of 3,000 patients.

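### The zero CHA2DS2-VASc group in section 5.2 admits men aged 65 to 74, who score 1 in the section 8.4 table

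*Combined protocol and SAP*

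**What the plan says.** Section 4.2 lists as a secondary objective "To determine the negative predictive value of the CHADS2VASC score of cardiac thrombus risk in the study population". Section 5.2 turns this into an outcome, "Number of patients with atrial thrombus among patients with a zero CHADS2VASC score", and explains in brackets who has a zero score: none of heart failure, hypertension, diabetes or vascular disease, and then "history of stroke or transient ischemic attack, age under 75, and male". The CHADS2 item that follows uses the same age limit: "history of stroke or transient ischemic attack, and age under 75".

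The CHA2DS2-VASc table in section 8.4 gives 1 point for age 65 to 74, 2 points for age 75 or over and 1 point for female sex. It also scores "CHF or LVEF ≤ 40"% (1 point) and "Stroke/TIA/Thromboembolism" (2 points). The CHADS2 table in the same section gives its age point only above 75.

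Section 11.2 sets out the accuracy analysis for the ATE score and mentions neither CHADS score.

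**The concern.** The two sections disagree about who has a zero CHA2DS2-VASc score. The outcome definition stops at 75, whereas the scoring table already gives a point from 65. A programmer who codes the outcome as 5.2 writes it will put men scoring 1 into the group reported as scoring 0. The published NPV would then carry a label that the protocol's own table contradicts, whether or not the number itself moves. No section says that 8.4 takes precedence.

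There are two smaller mismatches. Section 5.2 leaves out low ejection fraction and thromboembolism other than stroke or TIA, both of which 8.4 scores. For CHADS2, a patient aged exactly 75 with no other factor is zero in 8.4 but outside the zero group in 5.2.

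**Working it through.** **Step 1. Compare the definitions.** The table takes a man with no heart failure, hypertension, diabetes, stroke or TIA, or vascular disease.

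| Age | Section 5.2 | CHA2DS2-VASc points, section 8.4 |
|---|---|---|
| under 65 | zero | 0 |
| 65 to 74 | zero | 1 |
| 75 or over | not zero | 2 |

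**Step 2. Enumerate.** Every whole year of age from 18 to 90 was crossed with all combinations of six yes/no items: female sex, heart failure, hypertension, diabetes, stroke or TIA, and vascular disease. Each profile was scored by the 8.4 table and checked against the 5.2 description.

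- Profiles that meet 5.2 and score 0: 47 (ages 18 to 64).
- Profiles that meet 5.2 and score 1: 10 (ages 65 to 74).
- Profiles that score 0 but fall outside 5.2: none.

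On these items the error runs one way: 5.2 only adds patients who score 1. With age under 65 in 5.2, every profile that meets the description scores 0 and no true zero is lost. The counts 47 and 10 are years of age, not patients, so they say nothing about how many patients are misplaced.

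**Step 3. Items outside the enumeration.** A man under 65 with an ejection fraction of 40% or less but no recorded heart failure scores 1 in 8.4 and passes 5.2. One with a previous thromboembolism that was neither stroke nor TIA scores 2 and passes 5.2. For CHADS2 the clash is confined to age exactly 75, where 5.2 is the narrower definition.

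**Step 4. Size of the age effect.** Let s be the share of the 5.2 group aged 65 to 74, r1 their thrombus rate, and r0 the rate at a true zero score.

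- NPV at a true zero score = 1 - r0
- NPV in the mixed group = 1 - [(1 - s) × r0 + s × r1]
- Shift = -s × (r1 - r0)

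The documents give no age distribution and no thrombus rate by score, so s, r0 and r1 are assumptions. The one anchor is the overall rate in section 11.1, "about 2 % of patients eligible to atrial fibrillation ablation", used as the upper value of r1. With r0 = 0.5%, the shift in percentage points is:

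| r1 | s = 15% | s = 25% | s = 40% |
|---|---|---|---|
| 0.5% | 0 | 0 | 0 |
| 1% | -0.075 | -0.125 | -0.20 |
| 2% | -0.225 | -0.375 | -0.60 |

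For example, -0.40 × (2% - 0.5%) = -0.60 points. The NPV at a true zero score is 99.50%; in the mixed group it lies between 99.50% and 98.90%.

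**The case against.** The operative term in 5.2 is a zero score, and the age limit only appears in a bracketed explanation. Section 8.4 is the scoring table, and summing it to zero defines the group fully. The shared age limit in the CHADS2 item suggests a phrase carried over by mistake, although that is inference. An analyst who computes the score from 8.4 never meets the problem. **This stands in part:** the error is conditional on 5.2 being used. It does not remove the contradiction, because 5.2 is where the outcome is defined and nothing ranks the two sections.

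The stakes are limited. This secondary objective has no success criterion, and no comparison with the ATE score is planned. **This stands.**

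The size is almost wholly assumed. The 2% rate covers all patients, including those with heart failure, hypertension or previous stroke, so applying it to men with no other factor is an extreme case. Sampling error could also hide the shift: if the zero group held 600 patients with 3 thrombi (an assumption), the exact 95% interval for the thrombus rate would run from 0.10% to 1.45%. **This stands.** The direction of the misclassification is established; its size is not.

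Finally, the omitted ejection fraction and thromboembolism items may cost more than wording. Section 9.4 lists the data collected as "hypertension, diabetes, congestive heart failure, age, history of stroke, peripheral arterial disease and diagnosis", which names neither. **This stands as a query,** since the case report form is an appendix that was not available for this review.

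**Conclusion.** The concern holds. As written, section 5.2 gives a wrong zero group for a stated secondary outcome, and the plan's own table in 8.4 shows it. Men aged 65 to 74 with no other factor are added and no true zero is lost on the enumerated items.

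The numerical effect is conditional. There is none if the score is programmed from 8.4. If 5.2 is programmed, there is still none when the misplaced men have the same thrombus rate as true zeros; otherwise the shift reaches -0.60 percentage points at the far end of the assumed range. That range illustrates the scale and is not an estimate. The ejection fraction, thromboembolism and age-75 mismatches are minor. The primary ATE analysis uses neither age nor this score and is untouched.

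**What to change.** - In 5.2, change the CHA2DS2-VASc age condition to under 65.
- In 11.2, add one sentence stating that both scores are derived by program from the 8.4 tables, including the ejection fraction and thromboembolism items, and that the zero groups are patients whose derived score is 0.
- Use one CHADS2 age boundary in 5.2 and 8.4, so that age exactly 75 is classified one way.
- Query: confirm that the case report form captures every component of the 8.4 tables. Besides ejection fraction and other thromboembolism, the list in 9.4 does not name TIA, myocardial infarction or aortic plaque.

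The age corrections cost only wording, because age is already collected; they need no extra patients or procedures. The cost of the remaining items depends on the answer to the query.

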7.1. Inclusion / Exclusion criteria for intended population

Inclusion criteria

- Adult patients
- Patients hospitalized for ablation of atrial fibrillation or symptomatic left atrial tachycardia.
- Affiliated person or beneficiary of a social security system
- Who have signed or orally given an informed consent according to local regulation,

Exclusion criteria

- Contraindication to transoesophageal echocardiography,
- Transoesophageal echocardiography made in another centre than the centre of ablation,
- Pregnant women, parturient mothers and nursing mothers,
- Lives in an institution on court or authority order,
- Severely altered psychological health,
- Persons leaving in health or social establishment,
- Minors,
- Under guardianship,
- Persons unable to give their consent,
- Refusal to participate in the study.

